Statistical Methods For the correlation studies, global and regional MBF measurements acquired using SPECT and PET and calculated MFR measurements will be correlated with Spearman correlation analysis. For the reproducibility study, Bland-Altman plots will be used to determine significant bias and the coefficient of repeatability of global and regional MBF measurements acquired using SPECT and calculated MFR.

Abbreviations

3D	three dimensional
ACC	American College of Cardiology
AC	attenuation correction
AE	Adverse Event
AV	atrial-ventricular
BMI	body mass index
CABG	coronary artery bypass graft
CAD	coronary artery disease
CRF	case report form
COPD	chronic obstructive pulmonary disease
CT	computed tomography
g	gram
ICH GCP	International Conference on Harmonization Good Clinical Practice
kg	kilograms
kVp	kilo-volt potential
MBF	myocardial blood flow
MBq	megabequerels
mcg	micrograms
mCi	millicurie
MFR	myocardial flow reserve
mg	milligrams
min	minute
mm	month
MRN	medical record number
mSv	milliseverts
¹³ NH ₃	Nitrogen-13-ammonia
NC	no correction
NYHA	New York Heart Association
OHSN-REB	Ottawa Health Science Network Research Ethics Board
PET	positron emission tomography
PCI	percutaneous coronary intervention
PHI	Personal Health Information
⁸² Rb	Rubidium-82 Chloride
SAE	Serious Adverse Event
SC	scatter correction
SPECT	single photon emission computed tomography
SOP	Standard Operating Procedures
^{99m} Tc	Technetium-99m
²⁰¹ Tl	Thallium Chloride
TOH	The Ottawa Hospital
UOHI	University of Ottawa Heart Institute
yyyy	year

1. Introduction

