For the first time, [name] and our group recently demonstrated the accurate quantification of MBF in a pig model of rest and transient occlusion at stress [15]. Data were acquired using attenuation and scatter corrected dynamic SPECT data with a NM 530c camera with ^{201}TI , $^{99\text{m}}\text{Tc}$ -tetrofosmin and $^{99\text{m}}\text{Tc}$ -sestamibi. MBF was measured with gold-standard microspheres injected simultaneously with the SPECT tracers. Measured extraction fraction data agreed with those obtained previously using invasive techniques. MBF determined using the measured extraction fractions produced accurate values and good correlations with microsphere MBF between $r=0.75$ and $r=0.83$ ($p<0.01$ for all) and the resulting correlation in the MFR was up to 0.89 ($p<0.01$). Thus, non-invasive measurement of absolute MBF with a stationary dedicated cardiac SPECT is feasible using common perfusion tracers.

The goal of this study is to compare SPECT and PET measurement of MBF and MFR and determine the reproducibility of SPECT MFR measurements in patients.

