1.2 Hypothesis

1. The correlation of global and regional myocardial blood flow (MBF) measurements and calculated myocardial flow reserve (MFR) using SPECT to PET in participants with an intermediate to high probability of CAD will be $r > 0.6$ (Phase 1);
2. The test-retest reproducibility of global and regional MBF measurements and calculated MFR using SPECT in participants with an intermediate to high probability of CAD will be within 10 to 15% (Phase 2);
3. The correlation of global and regional MBF measurements and calculated MFR using SPECT to PET in normal volunteers will be $r > 0.6$ (Phase 3).

2. Study Objectives

1. To evaluate the correlation of global and regional MBF and MFR measured using SPECT to that measured using PET in participants with an intermediate to high probability of CAD (Phase 1);
2. To determine the reproducibility of global and regional MBF measurements and calculated MFR using SPECT in participants with an intermediate to high probability of CAD (Phase 2);
3. To evaluate the correlation of global and regional MBF and MFR measured using SPECT to that measured using PET in normal volunteers (Phase 3).

3. Study Design

Phase 1:

Patients referred to the University of Ottawa Heart Institute Diagnostic Imaging Department for myocardial perfusion imaging (MPI), PET or SPECT, will undergo a clinically indicated rest/stress PET scan using either Rb-82 or $^{13}\text{NH}_3$. Research imaging will consist of a rest/stress SPECT scan with $^{99\text{m}}\text{Tc}$ completed with 4 weeks of the PET scan, occurring either before or after the PET scan.

Study end will be defined as the completion of both the PET and SPECT scans.

Phase 2:

Patients will undergo a clinically indicated rest/stress SPECT scan as referred. Research imaging will consist of a second rest/stress SPECT scan with $^{99\text{m}}\text{Tc}$ within 4 weeks of the clinical SPECT scan.

Study end will be defined as the completion of both SPECT scans.

Phase3:

Normal volunteers will undergo a rest/stress PET scan using either Rb-82 or $^{13}\text{NH}_3$ and a rest/stress SPECT scan with $^{99\text{m}}\text{Tc}$ completed within a 4 week period.

Study end will be defined as the completion of both the PET and SPECT scans.

4. SPECT and PET Imaging

4.1 $^{99\text{m}}\text{Tc}$ SPECT Imaging

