Following acquisition, the listmode data will be rebinned into 9x10s, 6x15s, 4x120s frames. The projection data for each frame will be independently reconstructed using manufacturer supplied MLEM iterative reconstruction that includes point-spread function modeling and a noise-suppression prior. A total of 30 iterations will be used corresponding to the manufacturer recommendation for resting (low-count) studies. Images will be filtered post-reconstruction using a 3D 5th-order Butterworth filter with a cut-off frequency of 0.37 cycles/cm. Images will be reconstructed without corrections (NC), and with attenuation correction (AC) and scatter correction (SC). When applied, AC will be based on the CT scan from the PET/CT acquisition which will be coregistered manually to the emission reconstruction using on-line quality assurance tools. SC will be applied to the projection data prior to reconstruction using a dual-energy window approach [15]. For the Phase 2 SPECT reproducibility study, an additional CT scan will be acquired on an Infinia/Hawkeye 4 SPECT/CT gamma camera and used in place of the CT from the PET/CT acquisition.

The reconstructed dynamic image series will be processed using FlowQuant (Ottawa, ON), our in-house kinetic analysis software [17] as well as Infinia (GE Canada). With this semi-automatic software, a 1-tissue-compartment model will be fit to the myocardium time-activity data to generate a parameterized map of the uptake rate constant K1 (ml/min/g) for the heart. K1 values will be scaled to MBF based on the K1-MBF relationship determined from the pig studies (15). Finally, the results from the FlowQuant (Ottawa, ON) will be compared to those of the commercially released Infinia software (GE Canada) to determine the similarities between the two software packages.

4.2 ^{82}Rb / $^{13}\text{NH}_3$ PET Imaging

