4.3 Concentration of $^{99\text{m}}\text{Tc}$ SPECT tracer

SPECT perfusion tracers are known to bind to red blood cells limiting the amount of tracer available to the myocardium for extraction [15]. Thus, concentration function used in the kinetic analysis is better represented by the plasma concentration of tracer instead of the whole blood concentration, as measured by the image-based methods used in this study. Correction for the plasma to whole blood ratio can be done by applying a correction curve. The correction curve has been determined with pig experiments but needs to be calibrated to humans. To estimate this correction, we will measure the whole-blood to plasma tracer concentration ratio at equilibrium (~30min post injection) which will then be used to rescale the full curve that was measured in the pig study. For this purpose, a 12ml blood sample (2x6ml) at 30min after the rest tracer injection and a 2nd 12ml (2x6ml) blood sample at 30min will be drawn after the stress injection. Whole blood and serum aliquots will be prepared and then measured in a well-counter to determine the concentration ratio.

5. Sample Size and Statistical Analysis

The sample size for the correlation studies (hypotheses 1 and 3) was calculated to provide a 95% confidence interval around $r=0.6$ that excludes $r=0.25$, which is considered the upper bound of no correlation. To obtain a difference in the z-transform of $r=0.6$ and $r=0.25$ of 1.96 requires an n of 24. A withdrawal rate of 10 to 15 % increases the number of patients required to 30 per group.

The sample size for the reproducibility study (hypothesis 2) is estimated to detect a 10% difference on background of 15% variability (assuming a SPECT MBF uncertainty similar to the high end of PET variability). This requires a sample size of 26 (power = 0.95; alpha =0.05). A withdrawal rate of 10 to 15 % increases the number of patients required to ~ 30 per group.

Adverse events will be listed on an individual basis. All safety variables and demographic data will be tabulated with descriptive statistics, if appropriate.

For the correlation studies global and regional MBF measurements acquired using SPECT and PET and calculated MFR will be correlated with Spearman correlation analysis. For the reproducibility study Bland-Altman plots will be used to determine significant bias and the coefficient of repeatability of global and regional MBF measurements acquired using SPECT and calculated MFR.

6. Study Population

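### Phases 1 and 3 pre-specify only Spearman correlation for SPECT against PET, so no planned analysis estimates bias or limits of agreement

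*Combined protocol and SAP*

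**What the plan says.** - **Statistic, Phases 1 and 3.** Section 5 says "For the correlation studies global and regional MBF measurements acquired using SPECT and PET and calculated MFR will be correlated with Spearman correlation analysis". The Synopsis, under Statistical Methods, says the same: "global and regional MBF measurements acquired using SPECT and PET and calculated MFR measurements will be correlated with Spearman correlation analysis".
- **Objective.** Section 2 is worded to match, for Phase 1: "To evaluate the correlation of global and regional MBF and MFR measured using SPECT to that measured using PET in participants". Phase 3 uses the same wording for normal volunteers. Section 1.2 sets r > 0.6 for both phases.
- **Goal.** Section 1.1 ends more broadly: "The goal of this study is to compare SPECT and PET measurement of MBF and MFR". The same sentence adds SPECT reproducibility.
- **Agreement methods.** Section 5 and the Synopsis assign Bland-Altman plots, bias and the coefficient of repeatability to the reproducibility study alone. That is Phase 2, two SPECT scans per participant.
- **Origin of SPECT MBF.** Section 4.1: "K1 values will be scaled to MBF based on the K1-MBF relationship determined from the pig studies (15". Section 4.3 rescales the pig plasma-correction curve using participants' blood samples. No comparable check in humans is described for the K1-MBF step.
- **Choices left open.** Section 4.1 provides for uncorrected and corrected SPECT images: "Images will be reconstructed without corrections (NC), and with attenuation correction (AC) and scatter correction (SC"). Sections 4.1 and 4.2 name two software packages, FlowQuant and Infinia. Section 3 allows two PET tracers: Phase 1 patients "will undergo a clinically indicated rest/stress PET scan using either Rb-82 or" 13NH3, and Phase 3 likewise. Section 5 does not say which SPECT value enters the comparison or whether the tracers are pooled.

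**The concern.** Correlation and agreement answer different questions. A Spearman coefficient above 0.6 says that SPECT orders participants broadly as PET does. It does not say whether a SPECT flow in ml/min/g is close to the PET flow in the same person.

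This matters here because the study's rationale is absolute flow, and the SPECT scale comes from a conversion measured in another species. If that conversion were off by a common factor in humans, the paired PET values could reveal it. The planned statistic discards that information. The Phase 2 analysis cannot recover it, because a factor common to both SPECT scans drops out of their ratio.

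For MFR the mechanism is narrower. A constant factor cancels between stress and rest, whereas a non-linear conversion error need not. In either case, no SPECT-PET agreement estimate is planned for MFR.

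**Working it through.** **1. The plan's own figure.** Inputs from Section 5: r = 0.6, excluded value 0.25, z = 1.96.

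n = 3 + (1.96 / (atanh 0.6 - atanh 0.25))^2 = 3 + (1.96 / (0.6931 - 0.2554))^2 = 23.05, rounded up to 24.

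This matches the stated 24. At n = 24 the 95% CI around 0.6 is 0.259 to 0.808, which excludes 0.25. The sample size is not at fault.

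**2. What Spearman can register.** For any k > 0, the ranks of k x MBF equal the ranks of MBF, so the coefficient is exactly unchanged. The same holds for any strictly increasing transformation within one state. As an illustration, take one simulated sample of 30 lognormal pairs, with SPECT multiplied by k:

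| k | Spearman | Mean % difference, SPECT - PET |
|---|---|---|
| 0.5 | 0.731 | -67.5 |
| 0.7 | 0.731 | -36.9 |
| 1 | 0.731 | -2.4 |
| 1.3 | 0.731 | +23.2 |
| 2 | 0.731 | +63.2 |

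For MFR, (k x stress) / (k x rest) = stress / rest, so a constant cancels.

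**3. What an agreement analysis would deliver at n = 24.** The documents give no SD for SPECT-PET differences, so it is assumed. Model on the log scale: between-subject SD B, independent error SD e for each method, r = B^2 / (B^2 + e^2).

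- e = B x sqrt((1 - r)/r), and between-method SD = e x sqrt(2).
- At the planning value r = 0.6: SD = 0.23 (B = 0.20), 0.35 (B = 0.30), 0.46 (B = 0.40).
- SD = 0.15 is added as a favourable end. It corresponds to r = 0.89 at B = 0.30.

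Formulas:
- 95% CI half-width for the log mean ratio: t(23) x SD / sqrt(24) = 2.069 x SD / 4.899 = 0.422 SD.
- Limits of agreement around a mean ratio of 1: exp(+/-1.96 SD).
- CI half-width for each log limit: t(23) x SD x sqrt(1/24 + 1.96^2/(2 x 23)) = 0.732 SD.
- Chance that the CI for the mean ratio excludes 1 when the true ratio is 0.8: non-central t with parameter |ln 0.8| / (SD/sqrt(24)), where |ln 0.8| = 0.223.

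| SD | CI for mean ratio | Limits of agreement | 95% CI of upper limit | Ratio 0.8 told from 1 |
|---|---|---|---|---|
| 0.15 | /x 1.07 | 0.75-1.34 | 1.20-1.50 | >99.9% |
| 0.23 (r = 0.6, B = 0.20) | /x 1.10 | 0.64-1.57 | 1.33-1.86 | 99.5% |
| 0.35 (r = 0.6, B = 0.30) | /x 1.16 | 0.51-1.97 | 1.53-2.54 | 86% |
| 0.46 (r = 0.6, B = 0.40) | /x 1.22 | 0.40-2.47 | 1.76-3.47 | 62% |

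The ratio 0.8 is an illustration, not a prediction. Whatever its size, a constant ratio leaves Spearman unchanged.

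**The case against.** The strongest reply is that the analysis does what the protocol asks. The objectives, hypotheses and sample size for Phases 1 and 3 are all written as correlation, and the protocol calls them correlation studies. The gap appears only against the title and one sentence of the Background, where comparing need not mean agreement. This stands: the point is an omission measured against the broader goal, not a contradiction within the plan.

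Three stronger readings are tempting, and the documents support none of them.

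- *Agreement will go unreported.* Nothing bars further analyses, and the paired data will exist. The text supports only that agreement is not pre-specified. Agreement chosen afterwards would still be weaker evidence, given the open choices of reconstruction, software and tracer pooling.
- *SPECT MBF will be biased.* A conversion taken from pigs is a possible source of error. The documents neither give its functional form nor suggest an error of any size.
- *The protocol treats r > 0.6 as proof that SPECT equals PET in ml/min/g.* It makes no such claim.

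It can also be said that the study is small and that scans up to 4 weeks apart, with separate stress sessions, would mix between-day variation into the limits. Both are true. They restrict how the limits should be read, but they do not remove the value of estimating the mean ratio.

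**Conclusion.** The point holds as a gap in pre-specification. Followed as written, the plan would test whether SPECT and PET order participants alike. It could not show a constant or other order-preserving error in SPECT MBF at rest or at stress. The invariance is exact and rests on no assumption.

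What an added analysis would yield depends on a between-method SD that the documents do not supply. Over the assumed range of 0.15 to 0.46, the mean ratio would be known to within about /x 1.07 to 1.22 at n = 24. At r = 0.6, a true ratio of 0.8 would be distinguished from 1 in about 62% to 99.5% of trials as the assumed between-subject SD falls from 0.40 to 0.20. The mean ratio would therefore be informative, but the limits of agreement would be imprecise.

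This should be fixed. The planned correlation analysis remains valid for its own hypotheses.

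**What to change.** Keep Spearman for r > 0.6. Add to Section 5, for Phases 1 and 3:

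- A paired Bland-Altman analysis of SPECT against PET on the log scale, one value per participant, for global rest MBF, global stress MBF and global MFR.
- The mean SPECT/PET ratio and the limits of agreement, each with a 95% CI, presented as estimates rather than tests.
- One SPECT reconstruction and one software package, named in advance. The attenuation- and scatter-corrected reconstruction is a natural candidate, because of the pig work Section 1.1 says "Data were acquired using attenuation and scatter corrected dynamic SPECT data with a NM 530c camera".
- Pooled results, with results by PET tracer shown descriptively.
- If regional agreement is reported, an analysis done separately for each region or with a method that allows for several regions per participant. A Spearman coefficient pooled over regions needs the same care.
- A note that the limits include between-day variation as well as method difference.

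The cost is a few sentences and a modest extra analysis of data already being collected. The drawback is imprecise limits at n = 24 to 30, and still less precision by tracer.

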6.1 Source of Participants

The CAD study population will be adult male and female patients who are referred to the outpatient cardiology clinics and/or the non-invasive Diagnostic Imaging Department at the University of Ottawa Heart Institute (UOHI). The healthy volunteer population will be recruited from the Diagnostic Imaging Department or by the use of advertisements/posters located in UOHI and/or The Ottawa Hospital (TOH).

6.2 Inclusion Criteria

For all participants

- Age \geq 18 years old
- BMI \leq 40 kg/m²
- Able and willing to comply with the study procedures

Participants with intermediate to high probability of CAD

- Suspected or known CAD on a stable medication regime.

Healthy volunteers without known heart disease

- Low risk of CAD (ACC Guidelines Pre-test Probability of Coronary Disease by Symptoms, Gender and Age)

6.3 Exclusion Criteria

- History or risk of severe bradycardia (heart rate $<$ 50 beats per minute) not related to chronotropic drugs
- Known second- or third-degree AV block without pacemaker
- Dyspnea (NYHA III/IV), wheezing asthma or severe COPD
- Coronary artery bypass graft (CABG) surgery within 60 days prior to screening or at any time after consent
- Percutaneous coronary intervention (PCI) within 30 days prior to screening or at any time following consent

- Acute myocardial infarction or acute coronary syndrome within 60 days prior to screening or at any time following consent
- Recent use of dipyridamole-containing medications (e.g. Aggrenox)
- Known hypersensitivity to dipyridamole
- Breastfeeding or pregnancy
- Claustrophobia or inability to lie still in a supine position
- Unwillingness or inability to provide informed consent

6.4 Withdrawal from Study

Participants may withdraw from the study at any time without penalty or prejudice. No data will be collected from the time of withdrawal.

6.5 Early Termination

Participants may be terminated for reasons such as, but not limited to:

- Noncompliance with study procedures.
- Participant experiences a cardiac event.
- Secondary illness requiring intervention during the study.
- Pregnancy.
- Participant safety may be compromised in the opinion of the investigator.
- Study may be stopped at the request of a regulatory authority or the REB.

If study discontinuance occurs, the date and reason must be documented in the CRF. If the participant is lost to follow-up, documentation must be made as to the steps taken to contact the participant. Every attempt will be made to perform end of study follow-up with the participant who withdraws or is terminated.

7. Data Collection

All participant information and data will be collected respecting participant confidentiality and privacy and following written informed consent.

7.1 Demographic Information

Demographic information will include the participant's date of birth (mm/yyyy), gender, height and weight.

7.2 Medical History

Medical history and results from any standard of care testing related to a participant's cardiovascular disease and inclusion/exclusion criteria will be collected. Clinical data obtained at scan visits will be included as part of the study data.

7.3 Clinical Status

The blood pressure, heart rate and clinical status will be monitored according to current clinical protocols during imaging procedures. Clinical protocol will be followed for dipyridamole stress testing.

7.4 Caffeine Ingestion

The ingestion of caffeine will be restricted for 24 hours prior to all imaging procedures as per standard clinical practice.

7.5 Pregnancy Assessment

A woman of child bearing potential will have a urine pregnancy test performed on the days of imaging.

8. Risk Benefit Assessment

8.1 SPECT and PET Imaging

Phase 1:

Participants undergoing SPECT/CT imaging with ^{99m}Tc will receive a total radiation dose of 10.5 mSv (rest dose 2.8 mSv and stress dose 7.7 mSv)

Phase 2:

Participants undergoing research SPECT/CT imaging with ^{99m}Tc will receive a total radiation dose of 10.9 mSv (rest dose 2.8 mSv and stress dose 7.7 mSv) and one SPECT CT attenuation scan (0.4 mSv)).

Phase 3:

Participants undergoing PET imaging with Rb-82 and SPECT imaging with ^{99m}Tc will receive a total radiation dose of 12.6 mSv (10.5 mSv for the SPECT and 2.1 mSv for the PET, including low-dose CT (0.4mSv) attenuation scan).

Participants undergoing PET imaging with $^{13}\text{NH}_3$ and SPECT imaging with ^{99m}Tc will receive a total radiation dose of 12.3 mSv (10.5 mSv for the SPECT and 1.8 mSv for the PET, including low-dose CT (0.4mSv) attenuation scan).

8.2 Dipyridamole Pharmacological Stress

Dipyridamole is a vasodilator commonly used in the clinical practice of nuclear cardiology and will be used as the stress agent for all stress studies. Rare serious adverse reactions associated with the administration of intravenous dipyridamole for MPI have been reported. These have included fatal and non-fatal myocardial infarction, ventricular fibrillation, symptomatic ventricular tachycardia, stroke and transient cerebral ischemia. The infusion rate is monitored to minimize this risk and the symptoms can generally be reversed with an intravenous injection of 50 - 250 mg of aminophylline over several minutes.

9. Safety and Tolerability

9.1 Safety Variables

Safety variables will include the occurrence of procedure-related adverse events and changes in clinical status.

9.2. Safety Reporting

Adverse events (AE) and Serious Adverse Events (SAE) will be defined and reported according to ICH/GCP and Regulatory Standards. AEs and SAEs will be reported from the signing of the consent and followed until resolution or determined to be not clinically significant.

